13.3 Statistical Methods

13.3.1 Safety

The safety of device implantation in males 19-59 years of age will be evaluated.

Adverse events will be tabulated, graded for severity and relationship to the study products, and categorized by body system and the preferred term (MedDRA), and compared between groups. The number and percent of subjects with adverse events will be tabulated by body system, preferred term and treatment group. A similar summary will be provided for subjects with serious adverse events.

Hematologic and biochemical toxicity data will be summarized according to the criteria for toxicity described herein.

13.3.2 Osteogenicity

The osteoinductive nature of the experimental device will be evaluated.

13.4 DATA MANAGEMENT

Clinical data reported on CRFs and/or relevant serological/biological sample analysis results will be integrated into the internal clinical data management system at Agenta.

13.4.1 Data Processing

For each batch of data, double entry, quality control and triggers to computerized logic and/or consistency checks will be systematically applied in order to detect errors or omissions. After integration of all corrections in the complete set of data, the database will be locked and saved before being released for statistical analysis. Each step of this process will be monitored through the implementation of individual passwords and/or regular backups in order to maintain appropriate database access and guarantee database integrity.

14. SAFETY REVIEW COMMITTEE

The Safety Review Committee (SRC) will be established to review all safety data and make recommendations to Agenta regarding the continuation of the trial. This group may recommend trial continuation as scheduled, modifications to the current enrollment plan and/or cessation of device implantation.

14.1 Member Selection

The SRC will be comprised of 3 members, including the Principal Investigator, the Medical Monitor and a third member selected by the PI. [name], the sponsor's PI, will chair the SRC.

14.2 Meeting Schedule/ Adverse Event Review

The SRC will have a scheduled meeting at least once per week during the period of active enrollment and follow-up for each enrolled participant to 42 days. All members of the SRC will review the safety data weekly. Scheduled meetings may be cancelled at the agreement of all three SRC members if there are no safety issues to discuss. The SRC will hold a meeting to review the Day 7 data for the first 3 subjects, and the Day 7 safety data for each subject for the remaining 9 subjects. The SRC will recommend to either continue enrollment or termination of enrollment based on the safety and tolerability of the study product. All AEs that are moderate or mild will be submitted within 7 days from the site to the Study Medical Monitor. SAEs and severe adverse events will be reported within 24 hours after the clinical trial site is aware of the event.

The Medical Monitor will keep and maintain documentation for all SRC meetings with meeting minutes. Agenta personnel will tabulate the data for SRC review.

14.3 Stopping Rules

Stopping rules will be in place to arrest the enrollment process and suspend all experimental device placement with the occurrence of significant safety event(s). The stopping rules are:

- Any SAE or severe AE that is definitely, probably, or possibly related to the experimental device in the opinion of the investigator or Safety Review Committee.
- Occurrence of 3 or more moderate AEs of the same type that are definitely, probably, or possibly related to the study agent in the opinion of the investigator or Safety Review Committee.

The occurrence of AEs and SAEs will be monitored by the Medical Monitor who will notify the other members of the SRC if a condition is met to institute a stop rule. Enrollment and study agent administration cannot continue after a stop rule has been implemented until the SRC has reviewed the AEs and other subject safety data and made a recommendation to continue the trial as planned, modify the protocol or stop enrollment. The recommendation of the SRC must be reviewed and approved by Agenta.

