3. SCHEDULE OF EVALUATIONS

Visit Number	Screen	Visit 1	Contacts 1 and 2	Visit 2	Visit 3	Visit 4	Visit 5	Visit 6	Contact 3
Trial Timeline	Day -21 to 0	Day 0	Days 1 and 2 ¹	Day 3	Day 7	Day 42	Day 180 ¹	Day 360 ¹	Days 720 ¹
Visit/Contact Window (Days)	N/A	N/A	+/- 0	+/- 1	+/- 1	+/- 4	+/- 28	+/- 28	+/- 28
Informed Consent	X								
Inclusion/Exclusion	X	X							
Medical History	X								
Interim Medical History		X	X	X	X	X	X	X	X
Concomitant Medications	X	X	X	X	X	X	X	X	
Physical Examination	X								
HIV and Illicit Drug Test	X								
Physical Assessment: Vital Signs ² /Node Check		X		X	X	X	X	X	
Safety Labs (CBC, Blood Chemistry, PT, PTT, Urinalysis) ^{2,3}	X	X			X	X			
Surgical Treatment		X							
Surveillance (30 minutes)		X							
CT	X	X				X	X	X	
Diary Cards Distributed/Collected		X			X	X	X	X	X
Unsolicited Adverse Events		X	X	X	X	X	X	X	X

¹ Subjects will be contacted at Days 1 and 2, Days 42 and at 6 months, 1 year, and 2 years with a scripted telephone contact for safety follow-up and scheduling.

² Vital signs and laboratory values will be evaluated using the appropriate FDA draft guidance.

³ Any abnormal laboratory result arising post-administration, and of moderate or greater severity, will be followed until results return to baseline value or for the duration of safety follow-up.

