- e. Obtain blood samples (10 mL + 5 mL) and urine sample for clinical laboratory assessments.
- f. Obtain blood sample (4 mL) for PT and PTT tests.
- g. Collect and discuss diary card / distribute new diary card.
- h. Record AEs and SAEs.
- i. Set up appointment for Visit 4 (Day 42).

Visit 4 (Day 42)

- a. Confirm that the subject wishes to remain in the trial.
- b. Obtain interim medical history.
- c. Review diary card with subject.
- d. Record concomitant medication.
- e. Perform physical assessment (vital signs, lymph node exam, and symptom directed exam).
- f. Obtain blood samples (10 mL + 5 mL) and urine sample for clinical laboratory assessments.
- g. Obtain blood sample (4 mL) for PT and PTT tests.
- h. Record AEs and SAEs.
- i. Obtain radiographs and CT images of experimentally treated cranial defect.
- j. Set up appointment for Visit 5 (Day 180).

Visit 5 (Day 180)

- a. Confirm that the subject wishes to remain in the trial.
- b. Obtain interim medical history.
- c. Review diary card with subject.
- d. Record concomitant medication.
- e. Perform physical assessment (vital signs, lymph node exam, and symptom directed exam).
- f. Record AEs and SAEs.
- g. Obtain CT images of experimentally treated cranial defect.
- h. Set up appointment for Visit 6 (Day 360).

Visit 6 (Day 360)

- a. Confirm that the subject wishes to remain in the trial.
- b. Obtain interim medical history.
- c. Review diary card with subject.
- d. Record concomitant medication.
- e. Perform physical assessment (vital signs, lymph node exam, and symptom directed exam).
- f. Record AEs and SAEs.
- g. Obtain CT images of experimentally treated cranial defect.
- h. Set up appointment for Contact 3 (Day 730).

Telephone Follow-up (Day 730)

Study personnel (study coordinator or other personnel assigned by the investigator) will contact the participant to collect information on ongoing, previously recorded adverse events and new or ongoing SAEs. Reminder postcards will be mailed to each participant approximately one month prior to this contact. Study personnel will contact the participant by telephone approximately two weeks in advance of the follow-up target date to schedule a time for the telephone contact. During the telephone conversation, study personnel will collect interim medical history as well as update contact information.

Contact 3 (Day 730)

- a. Confirm that the subject wishes to remain in the trial.
- b. Obtain interim medical history.
- c. Record AEs and SAEs.

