11.1.2 Solicited Local and Systemic Events

All subjects will be given diary cards that are to be filled out for the purposes of recording any changes in health status after device administration.

- Diary Card #1 will be used to record all local and systemic events, as well as any other AEs that represent a change in the health status of the subject, from device placement through Visit 3 (Day 7).
- Diary Card #2 will be used to record unsolicited adverse events and SAEs through Visit 4 (Day 42).
- Diary Card #3 will be used to record unsolicited adverse events and SAEs after Visit 4 (Day 42) through Visit 5 (Day 180).
- Diary Card #4 will be used to record unsolicited adverse events and SAEs after Visit 5 (Day 180) through Visit 6 (Day 360).
- Diary Card #5 will be used to record unsolicited adverse events and SAEs after Visit 5 (Day 360) through Contact #3 (Day 720).

The diary cards will be considered the source document and will be transcribed into the case report form (CRF) by study site personnel. If the diary card is lost, this will be documented in the CRF, and the limited information collected during the clinic visit will serve as the source document. All other data points will be noted with "ND" (not determined).

For the purpose of collecting solicited local and systemic events, the following procedures will be implemented:

1. Study participants will be supplied with a digital thermometer on day 7 and shown how to use it to measure their oral temperature for weeks 1-6 following administration of the study product.
2. Participants will be asked to observe for AEs daily during the first 6 weeks post-implantation period. This includes systemic events including fever, chills, nausea/vomiting, weakness, muscle pain, and headache.
3. Diary Card #1 will be distributed during Visit 1 (Day 0) and collected during Visit 3 (Day 7). Diary Card #2 will be distributed during Visit 3 (Day 7) and collected during Visit 4 (Day 42). Diary Card #3 will be distributed during Visit 4 (Day 42) and collected during Visit 5 (Day 180). Diary Card #4 will be distributed during Visit 5 (Day 180) and collected during Visit 6 (Day 360). Diary Card #5 will be distributed during Visit 6 (Day 360) and collected by mail at Contact #3 (Day 720). Subjects will be asked

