11.1.4 Adverse Event Grading Scales

The severity of all adverse events will be graded as mild (Grade 1), moderate (Grade 2), severe (Grade 3), or potentially life threatening (Grade 4) according to the adverse event grading scale provided below. This grading scale will be used for local adverse events (those related to the cranial site of device administration) and systemic adverse events.

Mild (Grade 1)	Moderate (Grade 2)	Severe (Grade 3)	Potentially Life Threatening (Grade 4)
Symptom is present but does not interfere with activity	Symptom interferes with some activities but does not cause missed attendance at school or work	Incapacitating, unable to attend school or work or perform essential daily activities	Requires emergency room visit or hospitalization

Abnormal vital signs will be graded according to the above severity scale. This grading scale is based on the scale provided in the draft FDA guidance for industry, “Toxicity Grading Scale for Healthy Adult and Adolescent Volunteers Enrolled in Preventive Vaccine Clinical Trials” (April 2005).”

Any "severe" rating for local or systemic events requires the participant to call the study site for evaluation, the study site to notify the Medical Monitor (at the discretion of the investigator), and place comments on the AE page of the CRF that describe the event(s). Any severe adverse event that is deemed possibly, probably or definitely related to the study treatment will invoke a temporary stopping rule for the study to permit evaluation of the event by the SRC (see Section 14.3).

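### For moderate AEs that begin after Day 7, the stopping rule on three or more related moderate AEs can be delayed by about six weeks while device placement continues

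*Protocol*

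**What the plan says.** **The rule.** Section 14.3 states its purpose: "Stopping rules will be in place to arrest the enrollment process and suspend all experimental device placement". One of its two triggers is "Occurrence of 3 or more moderate AEs of the same type that are definitely, probably, or possibly related to the study agent". The Medical Monitor watches for the condition and alerts the rest of the Safety Review Committee (SRC).

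**How a moderate AE comes to light.**
- Section 11.1.2: "Diary Card #2 will be distributed during Visit 3 (Day 7) and collected during Visit 4 (Day 42". Subjects are to watch for AEs daily for the first six weeks.
- Section 3, footnote 1, on telephone contacts: "Subjects will be contacted at Days 1 and 2, Days 42 and at 6 months, 1 year, and 2 years". In Section 9.1 the visit after Day 7 is Day 42, with a window of ±4 days in Section 3.
- Section 11.1.4: a severe "rating for local or systemic events requires the participant to call the study site for evaluation". Nothing similar is required for a moderate rating. The standing instruction to call the site in Section 10.2 concerns SAEs.

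**How it travels on.** Section 14.2: "All AEs that are moderate or mild will be submitted within 7 days from the site to the Study Medical Monitor". Section 10.1 says the same. Neither says when the 7 days start. The faster route, also in Section 14.2, is: "SAEs and severe adverse events will be reported within 24 hours after the clinical trial site is aware of the event".

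**What runs alongside.** Section 14.2 has the SRC meet at least weekly during active enrolment and until each participant reaches 42 days. Section 7.1 limits accrual to one subject per week for the first three only. Subjects 4 to 12 follow after Day 7 review of those three, with no stated rate.

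**The concern.** The rule needs moderate AEs to be counted as they occur, but the collection schedule handles them as routine data once Day 7 has passed. The subject records the event, yet nothing requires anyone at the site to see it until the Day 42 visit. The weekly SRC review can therefore meet several times with no scheduled input on moderate AEs from a subject between Days 8 and 41.

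The period matters on the protocol's own account. Section 5.3 wants most of the biologic load released between 4 and 14 days, which straddles Day 7, and Section 5.5 states that there is no previous human experience with this plasmid approach. Related events after Day 7 are plausible. At stake is whether further subjects receive the device after the protocol's own pause condition has been met but before anyone can know it.

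**Working it through.** The protocol gives no operating figure for this rule. The probabilities in Section 13.1 concern seeing SAEs in a group of 10 and do not bear on timing. The check is calendar arithmetic.

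**Delay for one event.** Inputs: onset on Day 8 (first day of the gap); card collected on Day 42, or Day 38 to 46 with the window; 7 days from site to Medical Monitor. Assumption: the 7 days run from the Day 42 visit.
- Unknown to the site: 42 − 8 = 34 days (38 − 8 = 30; 46 − 8 = 38).
- Unknown to the Medical Monitor: 42 + 7 − 8 = 41 days (38 + 7 − 8 = 37; 46 + 7 − 8 = 45).

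**Delay for the rule.** Assumptions: subjects 1 to 3 implanted on calendar days 0, 7 and 14; each has the same related moderate AE on post-implant Day 8; none calls the site.
- Condition met: 14 + 8 = day 22.
- Third card collected: 14 + 42 = day 56. Third report due: 56 + 7 = day 63 (day 67 with the +4 window).
- Delay: 63 − 22 = 41 days (67 − 22 = 45).

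**Subjects implanted in between.** Subject 3 reaches Day 7 on calendar day 14 + 7 = 21, so enrolment can open on day 21, or on day 28 if review takes a week. Implants after day 22 and before day 63, for evenly spaced accrual at assumed rates:

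| Subjects 4–12 | Opens day 21 | Opens day 28 |
|---|---|---|
| one per 4 weeks | day 49: 1 | days 28, 56: 2 |
| one per 2 weeks | days 35, 49: 2 | days 28, 42, 56: 3 |
| one per week | days 28, 35, 42, 49, 56: 5 | the same: 5 |
| two per week | days 24.5 to 49: 8 | days 28 to 56: 9 |

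With a report on day 67, one per week adds day 63 and gives 6; one per 2 weeks opening on day 21 becomes 3; the rest do not change.

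**Which step causes the delay.** If the Medical Monitor learned of the third event on the day the card was collected (day 56), the counts would be 1, 2, 4 and 8 down the rows for either opening date. Most of the delay comes from the unobserved weeks, not from the 7-day submission.

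**The case against.** A reader might infer that the rule cannot act in time at all. The document does not support that. Through Day 7 there are in-hospital surveillance (Synopsis), contacts on Days 1 and 2, and visits on Days 3 and 7. The SRC reviews Day 7 data for the first three subjects before opening enrolment, and one criterion in Section 9.3 is a consistent pattern of AEs. Early moderate events are caught.

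Nor does protection vanish on Days 8 to 41. The SAE and severe-AE trigger works throughout, with calls by the subject and 24-hour reporting. Section 9.1 allows additional visits for any AE, and a subject may call unprompted. These routes can shorten the delay, but none is required for a moderate AE, and an extra visit presupposes that the site knows of the event.

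The 7-day submission is a maximum. The Principal Investigator sits on the SRC (Section 14.1) and can raise an event at the next weekly meeting. This stands, but it helps only once the site knows, and the count without those 7 days is still 1 to 8.

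The worked case combines unfavourable conditions: three subjects with the same event, onset on the first day of the gap, and no call. The accrual rate drives the result and is not in the protocol. At one implant per 2 to 4 weeks, 1 to 3 subjects are affected and the rule can still spare the others.

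A reader might also infer that the rule should count subjects rather than events. As written it refers to AEs, and a subject count would be harder to reach, not easier. The text does not say whether repeat entries by one subject count, so the unit needs stating, but this review does not choose it.

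**Conclusion.** The point holds for moderate AEs with onset after Day 7. On the scheduled data path, an event on Day 8 may be unknown to the site for 34 days (30 to 38) and to the Medical Monitor for up to 41 (37 to 45 with the visit window). The protocol meanwhile calls for weekly SRC review and sets no accrual limit for subjects 4 to 12. In the worked case, about 1–2 subjects are implanted after the condition is met at one per 4 weeks, 2–3 at one per 2 weeks, 5–6 at one per week, and 8–9 at two per week.

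These counts rest on the assumed implant dates, accrual rates, absence of spontaneous calls, and a 7-day clock starting at the Day 42 visit. They describe the scheduled worst case, not an expected outcome. No two sentences flatly contradict each other. The reporting arrangements simply do not supply what Section 14.3 needs during Days 8 to 41.

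**What to change.** Reconcile Sections 10.1, 11.1.2, 11.1.4 and 14.2 with Section 14.3, so that moderate AE data reach the Medical Monitor and the weekly SRC review during Days 8 to 41:
- In 10.1 and 14.2, send moderate AEs judged possibly, probably or definitely related by the 24-hour route already used for severe AEs, and state when the 7-day clock starts for the rest.
- In 11.1.4, have subjects report moderate as well as severe ratings to the site.
- In Sections 3, 9.1 and 11.1.2, add brief scripted calls between Days 7 and 42 using the Telephone Contact Symptom Assessment Form. Section 9.1 cites that form as Appendix D, but Section 17 lists only Appendix A, so confirm that it is attached.
- In 14.3, have the sponsor state whether the count is of events or subjects.

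If calls were weekly (Days 14, 21, 28 and 35), the third Day 8 event in the worked case would be found on day 14 + 14 = 28 and reported by day 29 instead of 63. Implants after day 22 and before day 29 would be 1 instead of 5 at one per week, and 1–2 instead of 8–9 at two per week.

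Cost: protocol wording, four short calls per subject at that frequency (4 × 12 = 48 in all), and more expedited reports for the Medical Monitor to handle. The threshold itself and the clinical response to it are left as they are.

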7.3 Reference Committees

A Safety Review Committee (SRC) will be utilized throughout this trial. The SRC is composed of the Principle Investigator, Agenta’s Medical Monitor, and a third member appointed by the Principle Investigator. The SRC will assess the progress of the clinical trial weekly and will determine whether to continue, modify, or stop the trial at protocol-specified intervals. The safety data review procedure used by the SRC is described in Section 9.3. The SRC is responsible for the clinical evaluation of the safety of the experimental bone graft device based on medical and ethical considerations. A detailed description of the responsibilities of the SRC is provided in Section 14.

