- d. Verify telephone contact information and mailing address and provide instructions to participant in the event of a change in contact information.

Additional Clinic Visits

Any subject with an abnormal laboratory result or who experiences an adverse event may be requested to come into the clinic for additional follow-up evaluation not specified by the protocol if this is deemed medically prudent by the investigator.

9.2 *Obtaining, Handling, Storage, and Shipment of Specimens*

9.2.1 *Blood Samples for Safety Laboratory Tests*

Blood samples collected for safety analysis will be labeled and handled per the local reference laboratory standard operating procedures for hematology and biochemistry profiles. Blood samples for safety laboratory tests will include one 5 mL and one 10 mL sample, as well as one 4 mL sample for PT and PTT testing where specified.

9.2.2 *Urine Samples*

A clean-catch urine sample will be collected by each participant for safety evaluation. Study personnel will be responsible for instructing subjects on this technique. Urine samples will be handled and labeled per the local reference laboratory standard operating procedures for urinalysis.

9.3 *Safety Data Review*

The SRC will perform a review of the safety data through seven days post-administration for the first three subjects, and through seven days post-administration for all subsequent subjects. The SRC will use the following evaluation criteria to approve the completion of enrollment after the first 3 subjects:

- a) Absence of SAEs or severe AEs "definitely", "probably" or "possibly" related to the experimental device.
- b) No evidence of severe hematologic or biochemical toxicity.
- c) No consistent pattern of AEs that, in the judgment of the SRC, represents a significant threat to the safety of the subjects with continued enrollment.

Approval from Agenta will be obtained before proceeding with treatment of subjects 4-12.

9.4 *Compliance with Protocol*

All participants who receive the experimental device will be included in the safety evaluation.

The following events are to be considered sufficient reason for discontinuation of a participant from the study:

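### The protocol gives inconsistent consequences, and inconsistent decision authority, for the same safety trigger

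*Protocol*

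**What the plan says.** **Triggers and hold.** Section 14.3 has two triggers. One is "Any SAE or severe AE that is definitely, probably, or possibly related to the experimental device", in the opinion of the investigator or the SRC. The other is "Occurrence of 3 or more moderate AEs of the same type", again at least possibly related. Either is to "arrest the enrollment process and suspend all experimental device placement". The hold lasts until the SRC has reviewed the data and "made a recommendation to continue the trial as planned, modify the protocol or stop enrollment". Then: "The recommendation of the SRC must be reviewed and approved by Agenta". Section 11.1.4 describes the pause for a related severe AE as temporary.

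**First three subjects.** Section 7.1 allows subjects 2 and 3 to be treated only if the 14.3 rules have not been met and no other safety concern exists. After the Day 7 data of the first three, it gives the SRC two outcomes: open enrolment to the other nine, or discontinue it. Section 9.3 lists the criteria for completing enrolment: (a) no related SAE or severe AE; (b) "No evidence of severe hematologic or biochemical toxicity"; (c) no consistent AE pattern that the SRC judges a significant threat. Sponsor approval is required before subjects 4 to 12 are treated.

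**Authority.** Section 7.3 says that the SRC "will determine whether to continue, modify, or stop the trial at protocol-specified intervals", and Section 7.1 also uses the verb *determine*. The synopsis and Sections 14, 14.2 and 14.3 use *recommend*.

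**Notification.** Section 11.1.4 leaves telling the Medical Monitor about a severe event to the investigator's discretion. Section 14.2 requires severe AEs to be reported within 24 hours. Section 14.3 relies on the Medical Monitor to tell the SRC that a stopping condition is met.

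**The concern.** Safety is the primary objective (Section 6.1), the trial is single-arm and unblinded, and Section 5.5 reports no earlier human experience with plasmid augmentation of perlecan domain 1. The pause and stop decisions are therefore a main protection for subjects. They also determine how many subjects contribute to the safety result. If two sections prescribe different outcomes for one event, the investigator, the sponsor and the IRB can each follow the protocol and disagree on whether the next subject may be treated. The number finally treated would then depend on which section was read.

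**Working it through.** **1. Follow one event.** Take a possibly related severe AE in subject 2, within seven days of implantation.

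| Section | Consequence for this event |
|---|---|
| 7.1, subjects 2 and 3 | A stopping rule is met, so subject 3 is not treated; no route to restart is given |
| 9.3(a) | A criterion for completing enrolment fails; unlike (c), it leaves no room for SRC judgement |
| 7.1, after three subjects | Open or discontinue; modification is not an option |
| 11.1.4 | Temporary stop while the SRC evaluates the event |
| 14.3 | Hold, then continue as planned, modify or stop |

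The last two rows permit what the first two rule out. No section says which prevails.

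**2. Who decides, and from what list.** The SRC determines in 7.1 and 7.3, and recommends in the synopsis, 14, 14.2 and 14.3. It has two options in the synopsis, 7.1 and 14.2, and three in 7.3, 14 and 14.3.

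**3. The interval after the recommendation.** The hold in 14.3 runs until the SRC has reviewed and recommended. Sponsor approval follows in a separate sentence and covers all three recommendations, including a stop. Nothing says whether the hold continues while approval is pending, or what follows if approval is refused. Section 9.3, by contrast, requires approval only to proceed.

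**4. Subjects 4 to 12.** Criteria (b) and (c) of 9.3 are written only for the decision after three subjects, and neither appears as a stopping rule in 14.3. Three protections remain for these nine subjects:
- SRC review of Day 7 data (9.3, 14.2);
- the rule on three or more related moderate AEs of the same type (14.3);
- any abnormal laboratory value that the investigator judges clinically significant, which is an AE under 11.1.5 and triggers 14.3 if severe and at least possibly related.

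The gap is therefore one of explicit criteria.

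**5. Notification.** SAEs go to the sponsor within 24 hours under Section 10.2 in any case. The conflict between 11.1.4 and 14.2 concerns severe events that are not serious, and any of these that is at least possibly related is a 14.3 trigger.

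**6. How often the conflict could arise.** The protocol's only safety probabilities (Section 13.1, n = 10) reproduce: at a 21% rate, 1 − 0.79^10 = 90.5% for at least one event; at 1%, 0.99^10 = 90.4% for none. They describe detection of events and do not bear on the decision rules. No rate is given for related SAEs or severe AEs, so the rates p below are assumptions, with subjects independent.

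| Assumed p | At least one in first 3: 1 − (1−p)^3 | At least one in 12: 1 − (1−p)^12 |
|---|---|---|
| 5% | 1 − 0.95^3 = 14.3% | 46.0% |
| 10% | 1 − 0.90^3 = 27.1% | 71.8% |
| 20% | 1 − 0.80^3 = 48.8% | 93.1% |

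The first column of results bears on step 1, with p taken as the rate by Day 7. The second bears on step 3, because any first-type trigger raises the approval question.

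**The case against.** **The sections serve different decisions.** Section 9.3 governs opening enrolment after subject 3, and 14.3 governs a pause at any time. They could be read together, with the stricter rule for the first three subjects. That is a reasonable reading, but the protocol does not state it. Section 14.3 offers continuation without excepting those subjects.

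**Determine versus recommend is minor.** Section 7.3 refers to Section 14 for the SRC's responsibilities, and Section 14 consistently says recommend. This weakens the point on authority. It does not explain the same verb in 7.1, and it leaves the status of enrolment pending approval open.

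**Subjects 4 to 12 remain protected.** This stands. A reader might infer that no laboratory or AE-pattern safeguard applies to them; the three protections in the working show otherwise.

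**Sponsor override.** A reader might infer that the sponsor can override a recommendation to stop. The protocol does not say so. The approval sentence can equally be read as a second lock, with placement halted until both bodies agree, and the approval to proceed in 9.3 fits that reading. What can be said is that the effect of pending or refused approval is undefined.

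**No effect at all.** A reader might infer that a trigger could leave the trial untouched. Section 14.3 always imposes at least a pause once a trigger is recognised, and resuming after review is not the same as no effect.

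**SRC membership.** "The SRC will be comprised of 3 members, including the Principal Investigator, the Medical Monitor and a third member selected by the PI". A reader might infer a defect in independence. Sections 7.3 and 14.1 agree on the membership and the protocol promises no independent board, so this is a design choice and no contradiction.

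**Conclusion.** The inconsistency is real and worth correcting. For a related SAE or severe AE in the first three subjects, 7.1 and 9.3(a) point to no further treatment, while 11.1.4 and 14.3 point to a temporary hold that may end in continuation as planned. The SRC's authority is worded in two ways, and the position between its recommendation and the sponsor's approval is not stated. The omission of 9.3(b) and (c) from 14.3 and the conflict on notification are lesser but related.

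The conclusion rests on the wording alone, and no protocol figure needs correction. The 14.3% to 48.8% range only shows that an event in the first three subjects is not remote. It depends on the assumed 5% to 20% rates and on independence between subjects.

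**What to change.** Reconcile the synopsis and Sections 7.1, 7.3, 9.3, 11.1.4, 14, 14.2 and 14.3 so that each of the following is stated once and cross-referenced elsewhere:

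1. the consequence of a related SAE or severe AE, before and after subject 3;
2. which criteria apply to subjects 4 to 12, and whether 9.3(b) and (c) are among them;
3. whether the SRC decides or recommends, and whether enrolment stays on hold while sponsor approval is pending or refused;
4. whether notifying the Medical Monitor of a severe event is mandatory.

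Which rule is right is for the sponsor, the investigator and the IRB.

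The cost is wording only: no added visit, sample or subject. Because the text concerns subject risk, it would not meet the description of an administrative change in Section 16.4 and would go to the IRB for approval as an amendment.
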